### ***SF -36***

The half-scale rule will be used to impute missing item responses in the SF-36 subscale scores i.e. a score will be computed if the responded answers at least 50% of items in that scale. The missing items in the scale will be imputed by the mean of the available items rounded to the nearest whole number.

The bodily pain subscale consists of Q7 and Q8 of the instrument. Since Q7 is based on 6pt Likert score and Q8 is based on a 5pt Likert scale and because mean imputation will be meaningless, the bodily pain subscale will not be imputed if any of the questions making up the scale is missing.

### ***EQ-5D-5L***

Index will be set to missing if any of the 5 dimensions is missing.

### ***MOS-Sleep***

MOS-Sleep subscale scores will be computed if at least 50% of items are available. The missing items will be imputed by the mean of available items.

### ***Western Ontario and McMaster osteoarthritis index (WOMAC)***

WOMAC scores will be computed when one pain item, one stiffness item, or at most 3 physical function items are missing. The missing items will be imputed by the mean of available items within the same subscale. The scores will be set to missing if more items are missing.

### **HealthCare Resource Use (HCRU) Questionnaire**

HCRU include the following categories

1. Use of walking aid over the past 8 weeks
2. Healthcare office visits over the past 8 weeks
  - a. Any use

- b. # of use
  - c. Any use related to OA
  - d. Any use related to CLBP
  - e. # of use related to OA
  - f. # of use related to CLBP
3. Emergency department (ED) visit over the past two months
- a. Any ED visits
  - b. # of ED visits
  - c. Any ED visit related to OA
  - d. Any ED visit related to CLBP
  - e. # of ED visits related to OA
  - f. # of ED visits related to CLBP
4. Hospitalization visit
- a. Any hospitalization
  - b. # of hospitalization
  - c. Length of hospitalization
  - d. # of hospitalization related to OA
  - e. # of hospitalization related to CLBP

### **Treatment Satisfaction Questionnaire for Medication (TSQM)**

**TSQM Scale scores** computed by adding the items loading on each factor. The lowest possible score is subtracted from this composite score and divided by the greatest possible score minus the lowest possible score. This provided a transformed score between 0 and 1 that should be multiplied by 100. (see below) *[Note that only one item may be missing from each scale before the subscale should be considered invalid for that respondent]*

- **EFFECTIVENESS**

$[(\text{Item 1} + \text{Item 2} + \text{Item 3}) - 3] \text{ divided by } 18) * 100$

***If one item is missing***

$[(\text{Sum}(\text{Item 1?} + \text{Item 2?} + \text{Item 3?})) - 2] \text{ divided by } 12) * 100$

- **SIDE-EFFECTS**

If Question 4 is answered 'No' then score = 100

Else...

$[(\text{Sum}(\text{Item 5 to Item 8}) - 4) \text{ divided by } 16) * 100$

***If one item is missing***

$(((\text{Sum}(\text{Item}5? \text{ to } \text{Item}8?)) - 3) \text{ divided by } 12) * 100$

- **CONVENIENCE**

$([\text{Sum}(\text{Item } 9 \text{ to } \text{Item } 11) - 3] \text{ divided by } 18) * 100$

*If one item is missing*

$(((\text{Sum}(\text{Item}9? \text{ to } \text{Item}11?)) - 2) \text{ divided by } 12) * 100$

- **GLOBAL SATISFACTION**

$([\text{Sum}(\text{Item } 12 \text{ to } \text{Item } 14) - 3] \text{ divided by } 14) * 100$

*If either Item 12 or 13 is missing*

$(((\text{Sum}(\text{Item}12? \text{ to } \text{Item}14?)) - 2) \text{ divided by } 10) * 100$

*If Item 14 is missing*

$(((\text{Sum}(\text{Item}12 \text{ and } \text{Item}13)) - 2) \text{ divided by } 8) * 100$

### **Beck Depression Inventory – II (BDI-II)**

The BDI-II total score is a sum of each of the 21 items rated on a 4-point scale ranging from 0 to 3 based on the severity of each item. The maximum total score is 63. Total Score of 0-13 is considered minimal range; 14-19 is mild; 20-28 is moderate, and 29-63 is severe depression.

### **Assessment of Peripheral vs. Central Pain**

The instrument assesses widespread pain as well as symptom severity. Widespread pain is a sum of the areas in which pain is indicated with a score ranging from 1- 19. Symptom severity is a measured on a scale of 1-12 by assigning points to responses according to the following rule:

No problem – 0 points; Slight or Mild Problem – 1 point; Moderate problem- 2; Severe problem -3;

And assigning a point of 1 to responses of ‘Yes’ for questions with a ‘Yes’/’No’ answer.

## **6.3. General Data Handling Conventions**

### ***Date of first/ last dose of study treatment***

The date of first injection is the first non-missing start date of dosing recorded in the eCRF.

The date of the last injection is equal to the last date of administration reported on injection administration case report form page or missing if the last administration date is unknown.

### ***Handling of Adverse Event and Injection Site Reaction Severity and relatedness***

If the severity of a TEAE is missing, it will be classified as “severe” in the frequency tables by severity of TEAEs.

If the assessment of relationship of a TEAE to the study drug or study conduct is missing, it will be classified as “related” to the investigation product.

### ***Handling of Missing/Incomplete AE/Concomitant Medication dates***

If the start date of an AE or concomitant medication is incomplete or missing, it will be assumed to have occurred on or after the intake of study medication, except if an incomplete date (e.g., month and year) clearly indicates that the event started prior to treatment. Thus, if the AE does not clearly indicate that the AE started prior to treatment or after the TEAE period, the AE will be classified as “treatment-emergent”. This is for classification purposes in the frequency tables and will not be used in the listings.

When only year is present, missing AE/concomitant medication end day and month will be imputed to the earlier of (study end date, 31DECYYYY).

When both month and year are present, missing AE/concomitant medication end date will be imputed to the last day of the month.

There will be no attempt to impute completely missing AE/concomitant medication end dates. Events with an end date missing will be assumed to be ongoing at the time of data cut off.

#### ***Handling of Adverse Events classification with missing or partial date/time of first study drug administration***

When the date and time of first study drug dose is missing, the date of randomization will be used as the start date for classification of AEs.

When the time of the first study treatment dose is missing, all AEs that occurred on the date of the first study drug dose will be considered as TEAEs.

#### ***Missing/Incomplete Medical history dates***

Medical history start dates are used to determine the duration of OA at baseline per eCRF data. Completing missing medical history dates will not imputed. Missing month will be imputed to January and missing day will be imputed to the first day of the month.

#### ***Laboratory Safety Variables below LLOQ or above ULOQ***

For central laboratory data below the lower limit of quantification (LLOQ), half of the lower limit value (i.e., LLOQ/2) will be used for quantitative analyses.

#### ***Missing laboratory, ECG, vital sign, physical exam, neurological exam***

No imputations for missing laboratory data, ECG data, vital sign data, physical examination, or neurological examination data will be made.

#### ***Handling of Potentially Clinically Significant Abnormalities (PCSA)***

If a patient has a missing baseline value they will be grouped in the category “normal/missing at baseline”.

For PCSAs with 2 conditions, one based on a change from baseline value and the other on a threshold value or a normal range, with the first condition being missing, the PCSA will be based only on the second condition.

For a PCSA defined on a threshold and/or a normal range, this PCSA will be derived using this threshold if the normal range is missing; e.g., for eosinophils the PCSA is  $>0.5$  GIGA/L or  $>ULN$  if  $ULN \geq 0.5$  GIGA/L. When ULN is missing, the value 0.5 should be used.

Measurements flagged as invalid by the laboratory will not be summarized or taken into account in the computation of PCSA values.

#### 6.4. Visit Windows

By-visit analysis (including efficacy, laboratory data, vital signs, ECG, ADA) will be summarized by the nominal visit number. Assessments taken outside of protocol allowable windows will be displayed according to the case report form (CRF) assessment recorded by the investigator. For assessments without a nominal visit number such as Unscheduled, 'EOT Week 16', and 'EOS Week 64' assessments, a visit number will be assigned based on the actual visit date using the study day analysis window based on the targeted visit study day in [Appendix 11.1 Table 2](#) Schedule of Events.

The following visit windows will be used to map the unscheduled visits, early end of treatment visits, early study termination visits and daily electronic diary entries, based on the study day:

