5. STUDY DESIGN

5.1. Study Description and Duration

This is a phase 3, randomized, double-blind, placebo-controlled, parallel-group study to evaluate the efficacy and safety of fasinumab in patients with moderate-to-severe non-radicular CLBP who have radiographically confirmed OA of the knee or hip, and who have a history of inadequate relief of their CLBP or intolerance to current analgesic therapy and inadequate relief of their CLBP from non-pharmacologic therapy. The study consists of a screening period of up to 30 days, a 7 (+3 day)-day pre-randomization period during which all pain medication except study-provided rescue medication will be discontinued, a 16-week treatment period (with the last Q4W dose of study drug administered at week 12), a 20-week follow-up period, and a final phone contact approximately 52 weeks after the last dose of study drug is administered ([Figure 1](#)).

Figure 1: Study Flow Diagram

EOS- End of study

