5.1.6. End of Study Phone Contact and Additional Imaging

Phone contact will be made approximately 52 weeks after administration of the last dose of fasinumab or placebo to document patient status with regard to JR surgery (if patient underwent, is scheduled for, or is on a wait list for JR surgery). Additionally, patients who had an AA confirmed during the study will have an MRI performed of the AA joint(s). If the AA joint(s) have undergone JR, an X-ray may be substituted for an MRI.

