### 1.1. Background/Rationale

This is a phase 3, randomized, double-blind, placebo-controlled, parallel-group study to evaluate the efficacy and safety of fasinumab in patients with moderate-to-severe non-radicular Chronic Low-Back Pain (CLBP).

The target population for the study are patients who have inadequate CLBP relief with acetaminophen/paracetamol, and who are unable tolerate or have inadequate CLBP relief with NSAIDs and opioids (or unwilling to take opioids) and who have inadequate CLBP relief from non-pharmacologic management. The target population for this study will also have concomitant radiographically confirmed OA of the knee or hip.

An unplanned interim analysis in the R475-PN-1524 study in patients with non-radicular CLBP showed evidence of efficacy with improvement in LBPI NRS pain scores in all fasinumab groups (6mg SC Q4W, 9 mg SC Q4W and 9 mg IV Q8W) compared to placebo at the 8 and 12-week timepoints.

At the time the protocol for this study was written, the maximum fasinumab dosages being evaluated in the OA program were 3mg SC Q4W and 6mg SC Q8W. The PK of fasinumab is described as linear, with concentrations in serum and exposure, as measured by similar area under the concentration-time curve (AUC), increasing in a dose-proportional manner. Therefore, the 6mg Q8W dose was expected to achieve similar AUC to that of the 3mg Q4W dose.

Therefore, in this target population of patients with CLBP with concomitant OA of the knee or hip, the 3mg SC Q4W dose or matching placebo was chosen as the dose regimen under study since 3mg was considered the maximum dose expected to be tolerable in CLBP patients who also had OA.

On May 3, 2018, following the independent and multidisciplinary fasinumab Data Monitoring Committee (DMC) review, the DMC recommended based on the risk benefit assessment of the entirety of the available data that higher dose regimens (3mg Q4W and 6mg Q8W) of fasinumab be discontinued across the OA program. As a result of this decision, dosing in this R475-PN-1612 evaluating the 3mg SC Q4W dose in patients with moderate-to-severe non-radicular CLBP who have radiographically confirmed OA of the knee or hip was discontinued for all patients who were still on study drug and the study was closed to enrollment.

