### 2.3. Study Plan

#### Study Visits

The study consists of a screening period of up to 30 days (Screening Period), followed by a 7 to 10 day pre-randomization period (Pre-Randomization Period), a 16-week randomized, double-blind, placebo-controlled treatment period (Treatment Period), a 20-week follow-up period, and an end of study phone contact at 52 weeks following the last dose of study drug to determine whether a joint replacement (JR) has been conducted or is scheduled (or the patient is on a waiting list). See [Figure 1](#) for the Study Flow Diagram.

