**Figure 1: Study Flow Diagram**

EOS- End of study

The Schedule of Events table is presented in [Appendix 11.1](#).

Prior to randomization, patients will undergo screening procedures. During the screening period, patients may continue to take their current pain medications.

Patients will then complete a pre-randomization period, during which all pain medication, except study-provided rescue medication (acetaminophen/paracetamol) will be discontinued.

Paracetamol/acetaminophen must not be taken within 24 hours prior to the randomization visit.

Following randomization (day 1), patients will enter into the treatment phase of the study during which study drug will be administered at scheduled visits and patients are permitted to use only acetaminophen/paracetamol as rescue medication. Use of acetaminophen/paracetamol is prohibited within 24 hours prior to the start of the study visits to minimize the confounding effects of the rescue medication on efficacy measurements. During the treatment period, efficacy and safety assessments will be performed at each study visit as outline in the schedule of events.

At the end of the 16-week treatment period, follow-up of patients will continue for an additional 20-weeks after the last treatment visit. Safety and efficacy assessments will be performed as outlined in the schedule of events.

Phone contact will be made approximately 52 weeks after administration of the last dose of study drug to document patient status with regards to JR surgery (if a patient underwent, is schedule for, or is on a waitlist for JR surgery).

The end of study is defined as the last phone contact for the last patient in the study.

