**Table 1: Visit Windows**

Visit No.	Visit	Targeted Study Days*	Analysis Window in Study Days
1	Screening	Day -30 to Day -11	$\geq -30$ and $\leq -11$
2	Pre-randomization Phone Call	Day -10 to -7	-10 to -1
3	Baseline #	1	1
4	Week 1	8	[2, 11]
5	Week 2	15	[12,20]
6	Week 4	29	[21,43]
7	Week 8	57	[44,71]
8	Week 12	85	[72,99]
9	Week 16	113	[100,127]
10	Week 20	141	[128,155]
11	Week 24	169	[156,183]
12	Week 28	197	[184,211]
13	Week 32	225	[212,239]
14	Week 36	253	[240,267]
15	Week 64	449	[436,456+]

\*Study days are calculated from the first dose of study drug (Day 1).

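### The end-of-study joint-replacement call is timed both from the last dose and at Day 449 from the first dose; the two agree only if the last dose was at Week 12, and the SAP visit window was not adapted after dosing stopped

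*SAP*

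**What the plan says.** **Timing from the last dose.** Protocol 5.1.6: "Phone contact will be made approximately 52 weeks after administration of the last dose of fasinumab or placebo". SAP 2.3 describes "an end of study phone contact at 52 weeks following the last dose of study drug" and, below the flow diagram, repeats: "Phone contact will be made approximately 52 weeks after administration of the last dose of study drug". The safety endpoint in Protocol 4.3 and SAP 4.5.1, and the Week 64 analysis in SAP 7, carry the same label of roughly 52 weeks after last dose.

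**Timing from the first dose.** The schedule of events (Protocol Table 1, SAP Table 2) puts the call at Week 64, Day 449 ±7. The SAP visit-window table (SAP Table 1) targets Day 449 with an analysis window of [436, 456+], and its footnote counts study days from the first dose.

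**How the record gets its visit.** SAP 6.4 names the Week 64 end-of-study assessment among those that carry no visit number of their own. For that group the rule is that "a visit number will be assigned based on the actual visit date using the study day analysis window". The window before Week 64 is Week 36, [240, 267].

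**What changed.** Protocol 5.1 planned a 16-week treatment period "with the last Q4W dose of study drug administered at week 12". SAP 1.1 reports that dosing "was discontinued for all patients who were still on study drug and the study was closed to enrollment", with 63 patients randomized by then. SAP 2.1 states that the plan takes account of this change.

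**The concern.** The two timings are interchangeable only for a patient whose last dose was given at Week 12. The study-wide stop means that some patients may have had their last dose earlier, and the SAP was written knowing this. It still kept a Week 64 window that presumes a Week 12 last dose.

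Hypothesis testing has been dropped (SAP 5.8), and patients are being followed to monitor safety (SAP 1.1). Apart from refreshing earlier outputs, the JR survey is the only analysis at the second database lock (SAP 7). With at most 63 patients the JR count will be small. How it reads depends on which calls are counted and how long after the last dose they were made. Imaging of patients with confirmed adjudicated arthropathy is tied to the same contact (Protocol 5.1.6 and 8.2.3.10).

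**Working it through.** **Inputs.** Nominal dosing days 1, 29, 57 and 85 (schedule of events). 52 weeks = 52 × 7 = 364 days. SAP Table 1 windows: Week 36 = [240, 267]; Week 64 = [436, 456+].

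**Reproducing the plan's figure.** Call day = last-dose day + 364. For a Week 12 last dose, 85 + 364 = 449, the scheduled day. Day 449 is therefore the last-dose timing evaluated for a patient dosed through Week 12.

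**The uncovered stretch.** Days 268 to 435 belong to no window: 435 − 268 + 1 = 168 days.

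**Both timings for each nominal last dose.**

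| Last dose | Call at last dose + 364 | SAP Table 1 window | Days before window opens (436 − call day) | If called on Day 449: weeks since last dose |
|---|---|---|---|---|
| Day 1 | 365 | none | 71 | (449 − 1)/7 = 64 |
| Day 29 | 393 | none | 43 | (449 − 29)/7 = 60 |
| Day 57 | 421 | none | 15 | (449 − 57)/7 = 56 |
| Day 85 | 449 | Week 64 | inside | (449 − 85)/7 = 52 |

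For a last dose before Week 12, a call made by the last-dose timing lands in the gap. A call made by the fixed schedule lands in the window, but 12, 8 or 4 weeks beyond the 52 in the endpoint's name.

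**Does the rate absorb the difference?** SAP 4.5.1 divides events by the duration of the observation period. If that is the period defined in SAP 5.6.3, it ends no later than the end-of-follow-up clinic visit, so time from that visit to the call is not in the denominator. Unequal call times would then not be adjusted for.

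**The case against.** **The by-visit rules may not govern this endpoint.** SAP 6.4 opens by referring to by-visit analyses and lists efficacy, laboratory, vital-sign, ECG and ADA data. JR is not on the list. SAP 7 identifies the endpoint by its source, the telephone survey, and SAP 5.9.2 calls for a listing of all JRs. The same section displays out-of-window assessments under the visit recorded on the CRF. This has force: an analyst could take the phone record directly and lose nothing. A reader might infer that unmapped calls will be dropped, but no text says so. What remains is that SAP 6.4 names the Week 64 assessment specifically and sends it to the date-based rule, so the point needs settling in writing.

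**Early discontinuers are asked to follow the fixed schedule.** The protocol synopsis asks patients who stop study drug to complete all planned assessments, including phone contacts, and the first schedule footnote encourages them to keep to the visit schedule. On that reading the call is on Day 449 and maps correctly. This stands, and it makes the empty-window problem conditional on which timing sites used. It does not remove the mismatch with the 52-week label.

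**Dose count is not the criterion.** A reader might infer that everyone with three or fewer doses is affected. Protocol 7.1 has a missed dose skipped and the next given on its scheduled date, so a patient who missed one dose but was dosed at Week 12 still reaches Day 449. The condition is when the last dose was given.

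**The tolerance cannot be borrowed.** A reader might also stack the ±7-day dosing and call windows to argue that every call after a Week 8 last dose must miss Day 436. The ±7 days for the call belongs to the Day 449 timing. The last-dose timing is only approximate and has no stated tolerance, so the result is shown for nominal days only.

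**Conclusion.** The concern holds in a limited form. The documents time one endpoint in two ways that agree only for a Week 12 last dose. For nominal last doses on Days 1, 29 and 57, the plan either sends the call to no window (Days 365, 393, 421) or measures a 52-week endpoint at 64, 60 or 56 weeks.

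This assumes nominal dosing days and 52 weeks taken as exactly 364 days. The documents do not give the number of patients affected; it lies between 0 and 63. Two stronger conclusions are not supported:

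- **Bias between arms.** The stop applied to all patients still on drug, and the documents give no distribution of last-dose dates by arm.
- **A flaw created by the dosing stop.** The two timings already differed for any early discontinuer under the protocol. The stop gives the mismatch wider reach, and the SAP did not take the opportunity to resolve it.

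Only the JR survey at the second lock is involved. The arthropathy endpoints and JR through Weeks 16 and 36 belong to the Week 36 analysis and are unaffected.

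**What to change.** 1. Reconcile the two timings of the call across Protocol 5.1.6, the schedules of events, SAP 2.3 and SAP Table 1, so that sites and analysts work from one anchor.
2. State in SAP 6.4 and 7 that the end-of-study phone-contact record is the JR survey whatever its study day, exempt from the SAP Table 1 window.
3. Derive weeks from last dose to the call, and report its distribution by arm beside the JR count.

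The cost is SAP wording, one derived variable and a clarification to sites. No additional patient contact or data collection is needed.

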**Table 1: Visit Windows**

Visit No.	Visit	Targeted Study Days*	Analysis Window in Study Days
1	Screening	Day -30 to Day -11	$\geq -30$ and $\leq -11$
2	Pre-randomization Phone Call	Day -10 to -7	-10 to -1
3	Baseline #	1	1
4	Week 1	8	[2, 11]
5	Week 2	15	[12,20]
6	Week 4	29	[21,43]
7	Week 8	57	[44,71]
8	Week 12	85	[72,99]
9	Week 16	113	[100,127]
10	Week 20	141	[128,155]
11	Week 24	169	[156,183]
12	Week 28	197	[184,211]
13	Week 32	225	[212,239]
14	Week 36	253	[240,267]
15	Week 64	449	[436,456+]

\*Study days are calculated from the first dose of study drug (Day 1).

# Baseline for the LBPI electronic diary entry will be mapped from day -7 to day 1.

If multiple measurements occur within the same visit window, the following rules will be used to determine the analysis value:

- When multiple valid measurements occur within the same visit window, the one closest to the target study day will be used in the analysis.
- When multiple valid measurements occur within equal distance from the target study day, the value after the target study day will be used in the analysis.

Both scheduled and unscheduled measurements will be considered for determining abnormal/PCSV values from laboratory, vital sign or ECG as well as the baseline values.

